8.2.2.5 Changes in ECOG performance score

The raw and change from baseline in ECOG performance score will be summarized for each assessment scheduled visit (i.e., Screening visit, Treatment Visits 1, 4, 7, 9, 11, Follow-up Visit 1

and Unscheduled Visit(s)). Descriptive statistics (n, mean, standard deviation, median, minimum and maximum) will be presented by treatment group. If the Normality assumption is met, t-test will be used to compare the mean of ECOG performance score between the treatment groups and if the Normality assumption is not met, a non-parametric method will be used.

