#### 3.3 ELIGIBILITY CRITERIA

#### 3.3.1 Inclusion Criteria

Subjects must meet all of the following criteria to be included in the study:

- 1. Patients diagnosed with AML or MDS per below:
  - Patients with a history of histologically or pathologically confirmed diagnosis of AML and < 5% blasts in the peripheral blood or bone marrow (per bone marrow aspiration and/or biopsy within 6 weeks prior to screening) scheduled to undergo allogeneic stem-cell transplantation
  - Patients with a histologically or pathologically confirmed diagnosis of MDS with
     10% blasts in the bone marrow (per bone marrow aspiration and/or biopsy within 6 weeks prior to screening) scheduled to undergo allogeneic stem-cell transplantation
- 2. Eastern Cooperative Oncology Group (ECOG) performance status score  $\leq 2$
- 3. Patients must have normal organ function as defined below:
  - Myeloablative allogeneic HCT:
    - Males and females, age  $\ge 18$  and  $\le 65$  years of age
    - Total bilirubin  $\leq$  2 mg/dL (except in patients with Gilbert's Syndrome)
    - AST/ALT  $\leq$  3 times institutional upper limit of normal (except in patients with leukemic infiltration of liver)
    - Serum creatinine  $\leq 2 \text{ mg/dL}$  and creatinine clearance  $\geq 60 \text{ ml/hr}$
    - Diffusing capacity of the lung for carbon monoxide (DLCO) > 50% predicted with no symptomatic pulmonary disease
    - Cardiac ejection fraction ≥ 50%. If between 40-49% a cardiology consult is required

CONFIDENTIAL Page 50 of 108

[figure not shown]
- Clinically normal resting 12-lead ECG at screening visit or, if abnormal, considered not clinically significant by the PI
- 4. Patients must have a reasonable expectation of  $\geq 6$  months survival
- 5. The donor-recipient HLA match criteria required for participation in this protocol are not research subjects in this study and they must meet criteria as National Marrow Donor Program (NMDP) donors. Procedures for selection of donors and stem cell dose will follow FDA requirements for Blood Products (21 CFR 640) and Human Cellular and Tissue Based Products (21 CFR 1271). The standard institutional practices for stem cell transplants also will be followed. The donors are:
  - o HLA-Identical Sibling (6/6): Minimal typing necessary is serologic typing for class I (AB) and molecular typing for class II (DRB1)
  - Matched Unrelated Donor (8/8): Molecular identity at HLA A, B, C and DRB1 by high-resolution typing

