## 8.6.4 Handling of Missing Data

For the per-protocol analysis of efficacy endpoints there will be no imputation of missing data. However, missing data will be imputed using methods that will be detailed in the SAP for the ITT population of the primary and secondary endpoints.

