6. ANALYSIS POPULATIONS

6.1 Intent-to-Treat Population

The Intent-to-Treat (ITT) population is defined as the set of subjects who are randomized to PRO 140 or placebo. The ITT population will be the primary analysis population for the analysis of primary and secondary endpoints.

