7.3 Handling of Missing Data

There will be no imputation of missing data for the analysis of efficacy and safety variables for this Phase II study.

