7.4 Sensitivity Analysis

For the analysis of the primary endpoint, a tipping point analysis will be conducted to assess the robustness of the results of the primary analysis and the impact of missing data.

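### The SAP gives no rule for how deaths enter the ECOG analysis, so the comparison defaults to survivors and can favour the arm with more deaths

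*SAP*

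**What the plan says.** Change in ECOG performance score is one of six secondary efficacy endpoints. Protocol 7.10, Table 7-1, defines an ordered scale from 0 to 5 in which 5 is death. Entry requires a score of 2 or less (protocol 3.3.1).

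SAP 8.2.2.5 summarizes the raw score and the change from baseline at screening, T1, T4, T7, T9, T11, Follow-up Visit 1 and unscheduled visits. The test is chosen by a Normality check. If Normality is met, a "t-test will be used to compare the mean of ECOG performance score between the treatment groups"; "if the Normality assumption is not met, a non-parametric method will be used". The fallback method is not named, no visit is named for the test, and the test sentence speaks of the score although the endpoint is the change.

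On missing values, SAP 7.3 states: "There will be no imputation of missing data for the analysis of efficacy and safety variables for this Phase II study". Protocol 8.6.4 says the opposite for these endpoints: "missing data will be imputed using methods that will be detailed in the SAP for the ITT population of the primary and secondary endpoints". The only sensitivity analysis for missing data is limited to the primary endpoint: "For the analysis of the primary endpoint, a tipping point analysis will be conducted" (SAP 7.4). SAP 6.1 adds: "The ITT population will be the primary analysis population for the analysis of primary and secondary endpoints".

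Neither document says whether a subject who dies is scored 5 at later visits or left without a score.

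**The concern.** No ECOG visit takes place after a death. With no imputation and no instruction to assign grade 5, a programmer following the SAP has only survivors' scores, although the population is labelled ITT. If deaths differ between arms, the ECOG comparison does not show it. If frailer subjects die more often, the arm that loses more of them is left with better-looking survivors.

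Deaths may not be rare. Protocol 1.2 cites transplant-related mortality of up to 20–30%, and protocol 9.1.10 sets a DMC review trigger at more than 20% mortality by day +100. ECOG is also the only efficacy measure whose scale includes death from any cause: SAP 7.9.7 counts only GVHD-related deaths as events in GVHD-free survival and censors the others.

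**Working it through.** **The plan's own figure.** There is none for ECOG. The only design figure is the confidence interval for GVHD incidence in SAP section 4 (50% against 15%, 30 per arm). It reproduces: 0.35 ± 1.96 × √(0.25/30 + 0.1275/30) = 0.130 to 0.570, width 0.44. It has no bearing on ECOG.

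**Inputs.** From the documents: 30 per arm and death = grade 5. Assumed, because the documents give neither: death rates of 10% against 20% or 30% by Day 98, and the scores subjects would have had if all had lived, with grades 0/1/2/3 at 27/40/23/10%. That distribution has mean 0.40 + 0.46 + 0.30 = 1.16. It is the same in both arms, so the drug has no effect on function. Differences below are the higher-death arm minus the lower-death arm; positive means worse.

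**1. Deaths unrelated to ECOG.** Survivors have mean 1.16 in both arms, so the survivors-only difference is 0.00. With deaths scored 5, the difference is (difference in death rates) × (5 − 1.16):
- 10% vs 20%: 0.10 × 3.84 = +0.38
- 10% vs 30%: 0.20 × 3.84 = +0.77 (+0.80 if the mean is 1.0)

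**2. Deaths commoner at poor ECOG.** Let the risk at grades 0/1/2/3 be 0.5/0.8/1.5/2.0 times the arm's death rate d. These multipliers average 1 over the distribution. The mean would-be score of those who die is 0.40×0.8×1 + 0.23×1.5×2 + 0.10×2.0×3 = 1.61. The survivors' mean is (1.16 − 1.61d)/(1 − d), and the mean with deaths scored 5 is 1.16 + 3.39d.

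| d | Survivors' mean | Mean, deaths = 5 |
|---|---|---|
| 10% | 1.110 | 1.499 |
| 20% | 1.048 | 1.838 |
| 30% | 0.967 | 2.177 |

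- 10% vs 20%: survivors only −0.06; deaths = 5, +0.34
- 10% vs 30%: survivors only −0.14; deaths = 5, +0.68

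Simulation of 5,000 trials per scenario agrees (−0.07 and −0.14; +0.33 and +0.68). The higher-death arm looked equal or better on survivors' scores in 60% and 71% of trials, against 23% and 7% with deaths scored 5.

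**3. All deaths from the worst scores (extreme case).** Take 30 subjects per arm with grades 0/1/2/3 in 8/12/7/3.
- 3 deaths: survivors 26/27 = 0.96; deaths = 5, (26 + 15)/30 = 1.37
- 6 deaths: survivors 20/24 = 0.83; deaths = 5, (20 + 30)/30 = 1.67
- 9 deaths: survivors 14/21 = 0.67; deaths = 5, (14 + 45)/30 = 1.97

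So 3 vs 6 deaths gives −0.13 on survivors and +0.30 with deaths = 5. For 3 vs 9 the figures are −0.30 and +0.60. Simulation with a slightly better distribution (30/45/20/5%) gave survivors-only differences of about −0.13 and −0.25.

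**4. Does the choice of test matter?** In the 3 vs 9 example on survivors' scores, the t-test gives p = 0.14 and the Mann-Whitney test p = 0.18, both in the direction favouring the arm with more deaths. The non-parametric fallback therefore does not cure the loss of the dead. The t-test itself does little harm: its simulated type I error at a nominal 5% was 0.050. It would also rarely be used, because Shapiro-Wilk rejected Normality in essentially every simulated sample of 30.

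**The case against.** A reader might infer three stronger things that the documents do not support.

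- *That ECOG is simply compared by t-test on an ordinal score.* The t-test is conditional, and the same sentence supplies a non-parametric alternative that would almost always apply. The check shows no harm from the t-test as such.
- *That the plan excludes the dead.* No text says so. Grade 5 is a valid grade, and recording it for a known death could be regarded as observed data rather than imputation. The survivors-only analysis follows from silence plus SAP 7.3, not from a stated exclusion. What stands is that the choice would be left open until someone programs it.
- *That the trial hides a difference in deaths.* It does not. Deaths are SAEs and are summarized as such (protocol 9.2, SAP 8.4.1). Discontinuations and their reasons are tabulated (SAP 8.1.1), GVHD-related deaths have a log-rank comparison (SAP 8.2.2.6), and mortality above 20% prompts DMC review. SAP 8.2.2.5 also reports n by arm at each visit. Only the ECOG comparison itself is blind to deaths.

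The sizes rest on assumed splits. The protocol's 20–30% is a background upper figure, and entry requires an expected survival of at least 6 months. Scoring deaths as 5 also makes a functional endpoint partly a mortality endpoint and does not give it much power. With deaths unrelated to ECOG at 10% vs 30%, a Wilcoxon test rejects in about 28% of trials and a Fisher test on deaths alone in 37%. In the 3 vs 9 example with deaths = 5, the rank test gives p = 0.65. The gain is the right direction, not a powered test, which is why deaths by arm should be shown beside it.

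**Conclusion.** The point holds as a missing rule for deaths, whichever test is run. Under the assumed 10% vs 20–30% deaths, the survivors-only comparison is off in one direction: from about 0.00 (deaths unrelated to ECOG), through 0.06–0.14 grade in favour of the arm with more deaths (frailer subjects die more often), to about 0.25–0.30 at the extreme. With deaths scored 5, that arm is 0.3–0.8 grade worse in the same scenarios. If deaths are balanced between arms and similarly related to ECOG, the bias is nil. This is one secondary endpoint in a proof-of-concept trial not sized by power, and the primary result is untouched, so it ranks as a worthwhile improvement rather than a necessary change. The disagreement between SAP 7.3 and protocol 8.6.4 on imputation for ITT secondary endpoints is plain on the page and needs no assumption.

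**What to change.** In SAP 8.2.2.5:

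1. Score a subject who has died as ECOG 5 (Table 7-1) at every scheduled visit after the date of death.
2. Compare arms with one named rank-based test, such as the Wilcoxon rank-sum test, with no Normality pretest.
3. Name the single visit at which the test is made. T11 (Day 98) is one candidate; the choice is the sponsor's.
4. State whether the raw score or the change from baseline is tested.
5. Show survivors-only summaries and the number of deaths by arm beside the test.

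Separately, reconcile SAP 7.3 with protocol 8.6.4, and state that grade 5 after death is an assigned grade under Table 7-1 and not an imputation.

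The cost is a few lines of SAP text and minor programming, since SAP 7.9.7 already uses dates of death. The downside is that the tested endpoint then combines function and survival; item 5 lets the reader separate the two.

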## 8.7.5 Efficacy Analysis

# 8.7.5.1 Primary Analysis

The primary analysis will be conducted on the ITT population.

The primary efficacy endpoint for this study is the incidence of  $\geq$  Grade II acute GVHD by Day - 100.

Chi-square/ Fisher's exact test will be used to compare the primary endpoint between the treatment groups.

All data from the secondary endpoints will be summarized and tabulated according to the variable type:

- Continuous data summaries will include:
  - O Descriptive statistics (n, mean, standard deviation, median, minimum and maximum) will be presented by treatment group
  - o For inferential statistics, if the Normality assumption is met, t-test will be used and if the Normality assumption is not met, a non-parametric method will be used.
- Categorical data summaries
  - o Frequencies and percentages will be presented by treatment group.
  - o For inferential statistics Chi-square or fisher's exact test will be used.

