3.1.2 Secondary Efficacy Endpoints

- Incidence of severe and life-threatening (Grade III and Grade IV) acute GVHD by Day-100
- Incidence of organ-specific acute GVHD by Day-100

- Donor engraftment evaluated by T-cell and myeloid chimerism in peripheral blood
- Neutrophil and platelet count recovery
- Changes in ECOG performance score
- GVHD-free survival (GFS)

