4. SAMPLE SIZE DETERMINATION AND RATIONALE, STATISTICAL POWER, AND SIGNIFICANCE LEVEL

For this two arm clinical trial, it is planned to have a total of 60 subjects (30 per treatment group). This is a proof of concept study, and sample size is on the basis of clinical judgment and not based on statistical power calculation. The number of subjects was deemed adequate to provide clinically meaningful descriptive results consistent with study objectives. Based on literature review, the incidence of GVHD in ablative transplant population range from 40-60%. Assuming that the control incidence of GVHD is 50% and that of the Active group is 15%, a sample size of 30 subjects per group produces a two-sided 95% CI for the difference in proportions with a width of 0.44 (i.e.,95% CI of 0.13 – 0.57).

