7. DATA CONVENTION AND RELATED DEFINITIONS

7.1 Baseline Definition

For all parameters, baseline will be defined as the last available value before treatment.

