7.7 Covariates and Prognostic Factors

There are no pre-planned covariates analyses of the data from this study.

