8.1 Summarizing and Tabulating the Collected Data

All data collected will be summarized according to the variable type:

- Continuous data summaries will include:
 - O Descriptive statistics (n, mean, standard deviation, median, minimum and maximum) will be presented by treatment group
 - For inferential statistics, if the Normality assumption is met, t-test will be used and if the Normality assumption is not met, a non-parametric method will be used.
- Categorical data summaries
 - o Frequencies and percentages will be presented by treatment group.
 - o For inferential statistics Chi-square or fisher's exact test will be used.
- Time-dependent data: Kaplan Meier methods will be used to analyze time dependent data and to depict the time to event data.

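### The ECOG test in SAP 8.2.2.5 does not say which variable or visit it applies to and, read literally, leaves out the baseline score already collected

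*SAP*

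**What the plan says.** Protocol 8.2.2 and SAP 3.1.2 both list the secondary endpoint as "Changes in ECOG performance score", and SAP 8.2.2.5 carries the same title. That section opens: "The raw and change from baseline in ECOG performance score will be summarized for each assessment scheduled visit". The visits it lists are Screening, T1, T4, T7, T9, T11, Follow-up Visit 1 and any unscheduled visit. If Normality holds, a "t-test will be used to compare the mean of ECOG performance score between the treatment groups"; otherwise a non-parametric method is used. The test sentence attaches neither raw nor change to the score and names no visit.

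Other provisions that bear on it:

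- SAP 7.1: "baseline will be defined as the last available value before treatment". Protocol 4.2.1 schedules ECOG among the pre-treatment assessments at T1, so for most subjects the T1 value should be the baseline.
- SAP 7.7: "There are no pre-planned covariates analyses of the data from this study". Protocol 8.6.3 says the same.
- SAP 8.1, for continuous data: "For inferential statistics, if the Normality assumption is met, t-test will be used", with a non-parametric fallback. Protocol 8.7.5.1 applies the same rule to the secondary endpoints: "All data from the secondary endpoints will be summarized and tabulated according to the variable type".
- Protocol 3.3.1 admits ECOG 0 to 2. Protocol 8.4 and SAP 7.8 stratify on donor source only.

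**The concern.** The first sentence of SAP 8.2.2.5 distinguishes two variables. The test sentence then uses the unqualified term, so a programmer could reasonably test the score, the change, or both, at any of several visits. The choices give different p-values, and nothing fixes in advance which one is reported.

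Taken literally, the test is a two-sample comparison of scores. Baseline ECOG varies by design, is not balanced by stratification, and is collected before the first dose, yet the specified comparison does not use it. In a trial of this size a chance baseline difference can move the result appreciably, and precision available at no extra data cost is given up.

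**Working it through.** **What can be reproduced.** The plan gives no SD, effect size or power for ECOG. Its one precision figure, in SAP section 4, concerns GVHD incidence: 0.35 ± 1.96 × √(0.5 × 0.5/30 + 0.15 × 0.85/30) gives 0.130 to 0.570, width 0.440, as stated. It does not bear on ECOG.

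**Inputs.** 30 per arm (SAP section 4). Two-sided tests (Protocol 8.7). A 5% level is used here; Protocol 8.7 prints 0.05%, a separate matter. The correlation ρ between baseline and follow-up ECOG is not in the documents and is varied from 0.2 to 0.8. Further assumptions: equal SD at baseline and follow-up, a linear model, a normal approximation, no missing data and no deaths. All results are in ECOG SD units.

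**Step 1: the three estimates.** Let D0 and D1 be the between-arm differences in mean ECOG at baseline and follow-up.

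- Score: D1
- Change: D1 − D0
- Baseline-adjusted: D1 − bD0, where b is the within-arm slope (equal to ρ under equal SDs)

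Randomisation makes the expected value of D0 zero, so all three have the same expected treatment difference. In one trial, the score and change estimates differ by exactly D0.

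**Step 2: how large D0 is by chance.** SE(D0) = √(2/30) = 0.258 SD.

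- P(|D0| > 0.25) = 2 × [1 − Φ(0.25/0.258)] = 0.333
- P(|D0| > 0.5) = 2 × [1 − Φ(0.5/0.258)] = 0.053

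**Step 3: what D0 = 0.25 SD does to each estimate.** The score comparison shifts by ρ × 0.25: 0.05 SD at ρ = 0.2 and 0.20 SD at ρ = 0.8. The change comparison shifts the other way by (1 − ρ) × 0.25: 0.20 SD at ρ = 0.2 and 0.05 SD at ρ = 0.8. The adjusted comparison does not shift under the linear model.

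**Step 4: precision.** Variance relative to the score is 1 for the score, 2(1 − ρ) for the change and 1 − ρ² for the adjusted comparison. With v the relative variance, the difference detectable at 80% power is (1.960 + 0.842) × √(2/30) × √v = 0.723 × √v.

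| ρ (assumed) | Score | Change | Adjusted |
|---|---|---|---|
| 0.2 | 0.723 | 0.915 | 0.709 |
| 0.5 | 0.723 | 0.723 | 0.626 |
| 0.7 | 0.723 | 0.560 | 0.517 |
| 0.8 | 0.723 | 0.457 | 0.434 |

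Power for a true 0.5 SD effect is 0.491 for the score at any ρ. At the four ρ values it is 0.334, 0.491, 0.705 and 0.865 for the change, and 0.507, 0.609, 0.774 and 0.898 for the adjusted comparison.

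The change comparison is less precise than the score when ρ is below 0.5. The adjusted comparison is more precise than both at each tabulated ρ.

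**The case against.** Three stronger readings are tempting, and the documents do not support them.

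- **That the raw score is definitely what is tested.** The test sentence does not say so, and it stands under a title that refers to changes. Literal wording favours the score; the title favours the change. The defect is that the text does not settle it.
- **That the change is never tested.** SAP 8.1 and Protocol 8.7.5.1 give a general t-test or non-parametric rule for continuous data that can cover the change, and SAP 8.2.2.5 does summarise change from baseline by arm. What is true is that no test sentence in 8.2.2.5 names the change.
- **That comparing scores answers a different question, or is biased.** A subject who enters at 2 and stays there ends with a worse score than one who goes from 0 to 1, yet has the better change. That ranks two individuals. Between randomised arms, the expected differences in score and in change are the same (Step 1).

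It can also be said that the trial is an unpowered proof of concept, that ECOG is one of six listed secondary efficacy endpoints, that the gain from adjustment rests on an unknown correlation, and that both documents plan no covariate analyses. All of this stands, and it limits the importance of the point. It does not supply the missing variable and visit, or give a reason to leave out a baseline already collected.

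**Conclusion.** The point holds as one of incomplete specification and avoidable imprecision. SAP 8.2.2.5 leaves the tested variable and visit open, and its literal reading is an unadjusted, though unbiased, comparison of scores. About one trial in three of this size would have a chance baseline difference above 0.25 SD, enough to shift the score comparison by 0.05 to 0.20 SD over the correlations considered.

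The benefit of adjustment ranges from negligible at a correlation of 0.2 (0.72 to 0.71 SD) to substantial at 0.8 (0.72 to 0.43 SD). These figures are a linear-model approximation with complete data. ECOG is ordinal, Protocol Table 7-1 assigns grade 5 to death, and SAP 7.3 plans no imputation, so they indicate direction and rough size only. The rank and proportional-odds methods proposed below were not evaluated separately. Sample size and the primary analysis are unaffected.

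**What to change.** In SAP 8.2.2.5, replace the test sentence with one that:

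- names the visit at which the arms are compared;
- compares follow-up ECOG between arms, adjusted for baseline ECOG as defined in SAP 7.1, by rank ANCOVA or a proportional-odds model, choosing one in advance;
- presents change from baseline by arm alongside.

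Record this as an exception in SAP 7.7. Reconcile it with Protocol 8.6.3, which also plans no covariate analyses, and with Protocol 8.7.5.1, which specifies a t-test or non-parametric method for continuous secondary endpoints; otherwise the SAP would conflict with the protocol.

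The cost is SAP wording, one additional model and the protocol reconciliation. No new data, visits or subjects are needed. Whatever method is chosen, the variable and visit still have to be stated.
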